5.3.5 Second Course *

All participants who stop study treatment with SD or better may be eligible for up to an additional 17 cycles (approximately 1 year) of pembrolizumab treatment if they progress after stopping study treatment from the initial treatment phase. This retreatment is termed the Second Course Phase of this study and is only available if the study remains open and the participant meets the following conditions:

Either

- Stopped initial treatment with study treatment after attaining an investigator-determined confirmed CR based on RECIST 1.1, and
 - Was treated with at least 8 cycles of study treatment before discontinuing treatment, and
 - Received at least 2 treatments with pembrolizumab beyond the date when the initial CR was declared

OR

- Had SD, PR, or CR and stopped study treatment after completion of 35 administrations (approximately 2 years) of study treatment for reasons other than disease progression or intolerance

AND

- Experienced an investigator-determined radiographic disease progression by RECIST 1.1 after stopping initial treatment, and
 - No new anticancer treatment was administered after the last dose of study treatment, and

- The participant meets all of the safety parameters listed in the inclusion criteria and none of the safety parameters listed in the exclusion criteria, and
- The study is ongoing

An objective response or disease progression that occurs during the Second Course Phase for a participant will not be counted as an event for the primary analysis of either endpoint in this study.

5.3.6 Chemotherapy extravasation

As a general recommendation, in the event of extravasation, the following advice should be considered:

- Stop the infusion immediately.
- Do not remove the needle or cannula.
- Aspirate with the same needle as much infiltrated drug as possible from the subcutaneous site.
- Apply ice to area for 15 to 20 minutes every four to six hours for the first 72 hours.
- Paint the skin over the extravasated site with 100% DMSO (or hyaluronidase) four times daily for two weeks.

Watch the area closely during the following days in order to determine whether a surgical excision and skin graft is necessary

5.4 General concomitant medication and additional assistance guidelines

Concomitant treatment and prior medication are defined as non-investigational medicinal product (IMP). Concomitant treatment includes any prescribed medication or phytotherapy between the 28 days prior to the administration of the first treatment dose and the last safety visit during treatment period. All concomitant treatments will be recorded. After this time, information will only be collected on any anti-cancer drugs taken by the patient until end of study.

Information on concomitant medication will include start date, end date, brand or generic name, route of administration, dose, and treatment indication. The following concomitant treatments are permitted during the study:

- Erythropoiesis-stimulating agents (ESA) (such as Procrit®, Aranesp®, EpoGen®) for the supportive treatment of anemia. Blood transfusions are permitted during the study.
- The prophylactic use of G-CSF is not allowed during the first treatment cycle, but can be used for cases of neutropenia arising during treatment, in accordance with the National Comprehensive Cancer Network (NCCN) guidelines.

- Bisphosphonates and denosumab for the prevention of skeletal events.
- Prophylactic or therapeutic anticoagulation therapy such as low-molecular weight heparin or warfarin at a stable dose level.
- Mineralcorticoids (e.g., fludrocortisone).
- Medications for the treatment of diarrhea, nausea, anorexia, or vomiting.
- Any medications deemed necessary to ensure patient safety and well-being may be administered at the discretion of the Investigator with the exception of prohibited therapies contained in **Section 5.5**.

5.5 Prohibited concomitant medications

Subjects are prohibited from receiving the following therapies during the screening and treatment phase of this trial:

- Immunotherapy not specified in the protocol.
- Chemotherapy not specified in the protocol.
- Endocrine therapy.
- Radiation therapy.

Note: Radiation therapy is allowed during screening, as long as it is completed at least two weeks prior to first dose of study treatment, and may be allowed to treat a symptomatic bone lesion or the brain after consultation with Sponsor.

- Herbal supplements.
- Live vaccines within 30 days prior to first dose of study treatment and while participating in the trial. Examples of live vaccines include, but are not limited to, the following: measles, mumps, rubella, varicella, herpes zoster, yellow fever, rabies, BCG, and typhoid (oral) vaccines. Seasonal influenza vaccines for injection are generally killed virus vaccines and are allowed. However, intranasal influenza vaccines (e.g., FluMist®) are live attenuated vaccines, and are not allowed.
- Immunosuppressive agents within seven days prior to first dose of study treatment.
- Steroids for any purpose other than to modulate symptoms from an event of clinical interest or suspected immunologic etiology.

Note: The use of physiologic doses of steroids (≤ 10 mg prednisone daily) is allowed and does not require Sponsor consultation.

Note: The use of systemic steroids to premedicate patients for whom computerized tomography (CT) scans with contrast are contraindicated is allowed. Magnetic resonance imaging (MRI) of

abdomen and pelvis with a non-contrast CT scan of the chest may also be performed in these patients.

Note: Local applications and inhaled steroids for management of asthma are allowed.

Subjects who, per Investigator's assessment, require any of the aforementioned medications for clinical management should be discontinued from study treatment. There are no prohibited therapies during the post-treatment follow-up phase.

5.6 Medication errors and overdose

Medication errors in this study may arise when the drug is administered at the wrong time or when the wrong dose strength is taken. Patient medication errors should be recorded on the relevant section in the case report form (CRF). In the event of an error in the administration of the medication, the Sponsor should be informed immediately.

Medication errors must be reported irrespective of the presence of an associated AE/SAE, including:

- Medication errors involving patient exposure to the IMP.
- Any possible medication errors or use of the medication not defined in the protocol which implicate the participating patient or not.

Regardless of whether the medication error is accompanied by an AE or not, in the judgment of the Investigator, the medication error should be recorded in the dose administration record page (DAR).

5.7 Treatment compliance

Patients will receive treatment under physician supervision. Personnel will check the administration volume and total administered dose. The administered dose of each treatment will be recorded in the source data and the appropriate CRF.

6 STUDY ASSESSMENTS AND PROCEDURES

6.1 Informed consent form

Written informed consent from the patient must be signed before performing any study procedure. However, tumor assessments available and performed as part of clinical practice prior to obtaining informed consent and within 28 days prior to treatment start may be used; such evaluations do not need to be repeated for screening.

By giving their consent, patients will be informed as to the nature of the study drug and will receive pertinent information regarding the study objectives, possible benefits, and potential AEs. They will also receive information on the follow-up procedures and possible risks they will be exposed to. This document also informs patients about how biological samples will be obtained and collected and its legal implications. After receiving the document, the patient will read it (or receive information verbally before witnesses) and will sign the previously approved informed consent. The patient will receive a signed copy of the informed consent. The patient can withdraw her consent and discontinue the study, this will not affect any future medical treatment. One re-screening is allowed in patients that are screening failure in this study. Patient has to re-consent ICF before any study procedure is done.

At inclusion:

- The Sponsor will request the patient's demographic and clinical data related to screening criteria. .
- Each patient will be given a Unique Patient Number (UPN) for this study, provided by the Sponsor. All data will be recorded in the appropriate CRF using this identification number. This number will be provided to the central laboratory to ensure traceability of study samples.

Confirmation of patient's eligibility for study participation will be recorded on the CRF. The Investigator is responsible for safeguarding patient information (e.g., age, name, address, telephone number, social security number, and study identification number), ensuring access to this information by HAs if necessary. These records will remain confidential for the period of time stipulated by current legislation.

6.2 Visit schedule

All screening tests and evaluations must be completed and reviewed to confirm that patients meet all eligibility criteria within 28 days prior to the first administration of study medication (dosing). Tumor assessments available and performed as part of clinical practice prior to obtaining informed consent and within 28 days prior to treatment start may be used; such evaluations do not need to be repeated for screening.

The Investigator will maintain a screening log to record details of all patients screened and to confirm eligibility or record reasons for screening failure, as applicable.

Visits are organized in programmed cycles of 21 days (if there are no delays in treatment owing to the occurrence of an AE). All visits must occur within \pm 2 working days (\pm 1 working day in day 8 of each cycle) from the scheduled date, unless otherwise noted in the schedule of assessments.

Assessments scheduled for day 1 (before treatment) of all cycles must be performed within 48 hours prior to study treatment administration and day 8 (before treatment) of all cycles must be performed within 24 hours prior to study treatment administration, unless otherwise indicated in the schedule of assessments, to confirm to the patient if treatment can be followed up. If a mandatory procedure described in the protocol falls on a bank holiday and/or weekend, this procedure should be performed on the day before or after the holiday (i.e. within a period of \pm 2 working days). The summary of all study assessments are included in **Appendix 1**.

Day 8 visits can be omitted, at the Investigator's discretion, in those patients that permanently discontinue eribulin treatment and continue with pembrolizumab as single agent.

End of treatment visit (EOT) will be performed within 30 days after last study dose and End of Study Visit (including survival status and post-study anticancer therapy evaluation) will take place 12 months after last study dose in the First Course of pembrolizumab phase treatment (\pm 14 days). Telephone contact is acceptable.

Participants who are eligible for retreatment/crossover with pembrolizumab (as described in Section 5.3.5) may have up to two EOT visits, one after the Initial Treatment Period and one after the Second Course Treatment.

Participants who are eligible to receive retreatment with pembrolizumab according to the criteria in Section 5.3.5 will move to the Second Course Phase when they experience disease progression. The same visits and evaluation calendar of the First Course will be followed during the Second Course Phase.

Follow-up visits

A follow up visit is required as per protocol to be performed to patients that finish the First Course Phase and are candidates to enter to the Second Course Phase of re-treatment with pembrolizumab, once disease progression is confirmed. A eCRF page will have to be completed in order to confirm the progression date. The tumor evaluation performed to confirm the progression disease before entering the Second Course Treatment will also be recorded at the eCRF.

During the period between the First and Second Course phases, it is highly recommended to perform safety follow up visits every 6 weeks and efficacy assessments every 12 weeks. However, patient's follow up during this period will be done as per local practice and at the Investigator criteria.

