3.3.1 Screening phase

During this phase, subject eligibility is determined, including the documentation of baseline characteristics. This phase of the study will begin once the informed consent is signed by the patient and the procedures to be performed are described in **Section 6** of the protocol.

One re-screening is allowed in patients that are screening failure in this study. Patient has to re-consent Informed Consent Form (ICF) before any study procedure is done.

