4.3 Exclusion criteria

Any patient meeting **ANY** of the following criteria will be excluded from the study:

1. Patients have received previous treatment with eribulin and an/or anti-PD1 or anti-PD-L1 agents.
2. Patients have a known hypersensitivity to any of the excipients of MK3475 (pembrolizumab) or eribulin.
3. Patients who have received chemotherapy, targeted small molecule therapy, or radiotherapy within two weeks of first dose of study treatment.

4. Patients who have received monoclonal antibodies for direct antineoplastic treatment or an investigational agent/device within four weeks of first dose of study treatment.
5. Patients have known active central nervous system (CNS) metastases and/or carcinomatous meningitis.

Note: Known brain metastases are considered active, if any of the following criteria is applicable:

- a. *Brain imaging during screening demonstrates progression of existing metastases and/or appearance of new lesions compared to brain imaging performed at least four weeks earlier.*
- b. *Neurological symptoms attributed to brain metastases have not returned to baseline.*
- c. *Steroids were used for brain metastases within 28 days of first dose of study treatment.*
6. Patients have peripheral neuropathy grade 2 or more.
7. Patients have a concurrent malignancy or malignancy within five years of study inclusion (with the exception of adequately treated basal or squamous cell skin carcinoma or curatively resected cervical cancer).
8. Patients have not recovered to grade 1 or better (except alopecia) from related side effects of any prior antineoplastic therapy.
9. Patients have had a major surgical procedure within 28 days prior to starting study drug.
10. Patients have an active cardiac disease or a history of cardiac dysfunction including any of the following:
 - Unstable angina pectoris or documented myocardial infarction within six months prior to study entry.
 - Symptomatic pericarditis.
 - History of documented congestive heart failure (New York Heart Association functional classification III-IV).
 - Patients have a left ventricular ejection fraction (LVEF) < 50% as determined by multiple gated acquisition (MUGA) scan or echocardiogram (ECHO).
11. Patients have any of the following cardiac conduction abnormalities:
 - Ventricular arrhythmias except for benign premature ventricular contractions.
 - Supraventricular and nodal arrhythmias requiring a pacemaker or not controlled with medication.

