6.4.2 Objective response assessment

CBR is defined as the proportion of the subjects in the analysis set who have a complete response, partial response, and stable disease using RECIST v.1.1 for at least 24 weeks.

ORR is defined as the proportion of the subjects in the analysis set who have a complete response or partial response based on RECIST v.1.1:

- Complete response: Complete disappearance of all targets lesions. Any pathological lymph nodes (target or non-target) must have reduction in short axis to < 10 mm.
- Partial response: At least a 30% decrease in the sum of diameters of target lesions, taking as reference the baseline sum diameters.
- Stable disease: Neither sufficient shrinkage to qualify for partial response, nor sufficient increase to qualify for disease progression, taking as reference the smallest sum diameters while on study.
- Disease progression: At least a 20% increase in the sum of diameters of target lesions, taking as reference the smallest sum diameters while on study. The development of new, previously undetected lesions, is also considered progression.

DoR is defined as the time from documentation of tumor response until disease progression or death from any cause.

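### The baseline tumor scan can precede radiotherapy or targeted therapy given up to two weeks before first dose, so shrinkage from earlier treatment could be counted as response and hence as clinical benefit.

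*Protocol*

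**What the plan says.** **Baseline scan.** Protocol 6.2 (and 6.1 in the same terms) allows tumor assessments "performed as part of clinical practice prior to obtaining informed consent and within 28 days prior to treatment start may be used", without repetition for screening.

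**Washout.** Protocol 4.3, exclusion 3, removes "Patients who have received chemotherapy, targeted small molecule therapy, or radiotherapy within two weeks of first dose of study treatment". Exclusion 4 sets a longer interval for other agents: "Patients who have received monoclonal antibodies for direct antineoplastic treatment or an investigational agent/device within four weeks of first dose of study treatment".

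**Screening restrictions.** Protocol 5.5 opens with "Subjects are prohibited from receiving the following therapies during the screening and treatment phase of this trial". Its list includes "Chemotherapy not specified in the protocol" and endocrine therapy. A note makes an exception: "Radiation therapy is allowed during screening, as long as it is completed at least two weeks prior to first dose of study treatment". Targeted small molecules are not on the list. On when screening starts, protocol 3.3.1 says: "This phase of the study will begin once the informed consent is signed by the patient".

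**Response.** Protocol 6.4.2 defines partial response as "At least a 30% decrease in the sum of diameters of target lesions, taking as reference the baseline sum diameters". Stable disease and progression are referred instead to the smallest sum seen on study. Protocol 8.2.1 counts best response by the local investigator and states no confirmation scan.

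**The concern.** A baseline for response should describe the disease as it stands when study treatment begins, with earlier treatment finished. Here a patient can be scanned on day -28, have a target lesion irradiated or take a targeted small molecule until two weeks before first dose, and still meet these criteria. The first on-study scan, at about week 9, is then compared with a sum measured before that treatment. A fall of 30% or more counts as partial response whichever treatment caused it.

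A partial response is clinical benefit by definition, so the primary endpoint is exposed. ORR uses the same responders, and DoR is computed among them. With one arm tested against a fixed 30%, no control group shares the error. The SAP would not catch it either. The deviation list in SAP 5.1 covers prohibited medication and tumor assessments out of window, and permitted radiotherapy after an in-window scan is neither. No planned sensitivity analysis addresses it.

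**Working it through.** **1. Width of the gap.** The scan may date from day -28 (6.2), and the washout in exclusion 3 is 14 days. Overlap = 28 - 14 = up to 14 days.

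**2. Which therapies fall into it.**

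| Therapy | 4.3 washout | 5.5, from consent | Can it follow the baseline scan? |
|---|---|---|---|
| Radiotherapy | 2 weeks | Allowed in screening if finished 2 weeks before first dose | Yes, up to 14 days |
| Targeted small molecules | 2 weeks | Not listed | Yes, up to 14 days |
| Chemotherapy | 2 weeks | Prohibited | Only if scan and dose both precede consent |
| Endocrine therapy | None stated | Prohibited | Only if scan and dose both precede consent; at most 28 days less the time from consent to first dose |
| Monoclonal antibodies, investigational agents | 4 weeks | Not relevant here | Essentially no |

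**3. Search for a safeguard.** Protocol 6.2, 6.4.1 and Appendix 1 footnote 3 set the window and type of imaging, but not its order relative to prior therapy. The requirement in inclusion 9 for a lesion not previously irradiated, sampled since last progression, applies to the biopsy. The protocol text has no rule on using an irradiated lesion as a target lesion. Appendix 2 cites RECIST v1.1 without reproducing it.

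**4. The plan's own figure.** Inputs from protocol 8.1: null 30%, target 50%, at least 17 of 39, 10% drop-out.
- Type I error: P(X ≥ 17 | n = 39, p = 0.30) = 0.04998.
- Power: P(X ≥ 17 | n = 39, p = 0.50) = 0.832, which meets the 80% target.
- Enrollment: 39 / (1 - 0.10) = 43.3, rounded up to 44.

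The design reproduces. The margin below 0.05 is practically zero.

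**5. Illustration of sensitivity.** Assume that k patients are counted as benefit solely through carry-over and that the rest benefit at the null rate. The false-positive rate at the printed rule is P(X ≥ 17 - k | n = 39 - k, p = 0.30). The 44-patient column uses at least 19, the smallest count with a one-sided p-value of 0.05 or less at that size (18 of 44 gives 0.081).

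| k | 17/39 | 19/44 |
|---|---|---|
| 0 | 5.0% | 4.4% |
| 1 | 7.6% | 6.6% |
| 2 | 11.3% | 9.7% |
| 3 | 16.3% | 13.8% |

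Alternatively, let a share f of patients without true benefit be miscounted, so that p = 0.30 + 0.70f. At 17/39 the rate is 6.1% (f = 1%), 7.4% (2%), 8.8% (3%), 12.3% (5%) and 24.4% (10%).

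The documents give no value for k or f. Both calculations leave out any effect that works against benefit.

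**The case against.** Several stronger readings are tempting, and the documents do not support them.

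- *A reader might infer that any patient could receive chemotherapy between days -27 and -15 and remain eligible.* After consent, section 5.5 prohibits it, and SAP 5.1 lists prohibited medication as a deviation to be reviewed. Only the pre-consent route remains.
- *A reader might infer a general 28-day overlap for endocrine therapy from its absence in 4.3.* Section 5.5 bars it from consent, so again only pre-consent treatment after a pre-consent scan qualifies.
- *A reader might infer that every response category depends on this baseline.* Section 6.4.2 uses the baseline sum as reference for partial response. Stable disease and progression refer to the smallest on-study sum, and DoR starts at documented response.
- *A reader might infer that the bias must favor a positive result.* Growth between an early scan and first dose makes a 30% fall harder to reach. Carry-over shrinkage also lowers the on-study nadir, so a 20% rise comes sooner and 24-week stable disease becomes harder to reach.

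It can also be said that miscounting faces a high bar. A partial response needs a 30% fall, first looked for at about week 9. The biopsy is normally taken after last progression, which suggests that most entrants have already progressed on their latest therapy. RECIST v1.1, which is not reproduced, may also govern the choice of target lesions.

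These arguments limit the scope and leave the size unknown. They do not close the radiotherapy and targeted-therapy routes, which need no pre-consent treatment. Prior targeted therapy is relevant in this population: SAP 6.4 plans subgroups by earlier CDK4/6, PI3K and mTOR inhibitor treatment.

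**Conclusion.** The gap is real but narrow. For up to 14 days, radiotherapy and targeted small molecules may follow the baseline scan. For chemotherapy and endocrine therapy this is possible only when both the scan and the treatment precede consent. Through the definition of partial response, earlier treatment could be credited to the combination in a single-arm test that has almost no type I error to spare.

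The frequency and the net direction are unknown. The rates of 7.6%, 11.3% and 16.3% for one, two or three affected patients show how sensitive the 17/39 rule is to such miscounts. They do not estimate the bias in this trial. They assume that every affected patient is a certain success and that all others benefit at 30%. The statement about target lesions concerns the protocol text only. This is an inexpensive improvement to the primary endpoint, and it does not invalidate the design.

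**What to change.** **Protocol 6.2, 6.4.1 and Appendix 1 footnote 3.** State that the baseline tumor assessment is scheduled after the last prior anticancer treatment. State also that a lesion irradiated between day -28 and first dose, whether before or after the scan, is not used as a target lesion. The second sentence is needed because a lesion irradiated on day -15 and scanned on day -13 would satisfy the first and could still be shrinking from the radiotherapy.

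**SAP.** Flag patients who received anticancer therapy between the baseline scan and first dose. Report CBR and ORR with these patients excluded, as a sensitivity analysis. Counting them all as non-responders serves only as a conservative bound, because it builds in the opposite bias. The data are already collected: protocol 5.4 records treatments from 28 days before first dose, and 6.3 records prior antineoplastic treatments and procedures. If accrual is already closed (its planned end was August 2018), this part can still be done.

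**Reconciliation.** Exclusion 3 and section 5.5 differ on chemotherapy, targeted small molecules and endocrine therapy in the weeks before first dose. The sponsor should make them agree; which rule applies is a clinical decision.

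**Cost.** Slightly tighter scan scheduling and one extra analysis. The 44 patients and the 17/39 rule stay as they are.
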